3.1. Endpoints

The primary endpoint of this study is:

- Clinical status assessed by a 7-point ordinal scale on Day 11

The secondary endpoint of this study is:

- The proportion of participants with treatment emergent adverse events

Other endpoints of interest are:

- The proportion of participants with negative SARS-CoV-2 polymerase chain reaction (PCR)
- Time to clinical improvement (days): clinical improvement is defined as a ≥ 2 -point improvement in clinical status (7-point ordinal scale) from Day 1
- Time to ≥ 1 -point improvement (days) from baseline clinical status
- Time to recovery: defined as an improvement in clinical status from a baseline score of 2 through 5 to a score of 6 or 7, or an improvement from a baseline score of 6 to a score of 7
- Time to modified recovery: defined as an improvement in clinical status from a baseline score of 2 through 4 to a score of 5, 6, or 7, or an improvement from a baseline score of 5 to a score of 6 or 7, or an improvement from a baseline score of 6 to a score of 7
- Time to room air: defined as an improvement in clinical status from a baseline score of 2 through 4 to a score of 5, 6, or 7
- Duration of oxygen therapy (days)
- Shift in oxygen support status from baseline
- Duration of hospitalization (days)
- All cause mortality at Day 28

- The proportion of participants in the Extension Treatment Group with treatment emergent adverse events

3.2. Study Design

Part A of this is a Phase 3 randomized, open-labeled, multi-center study RDV therapy in participants with moderate COVID-19. Eligible participants will be randomized in equal proportions to 1 of 3 treatment groups. No stratification will be performed. Part B is a single group multicenter study of RDV in participants with moderate COVID-19 infection.

3.3. Study Treatments

In Part A, approximately 600 participants who meet all eligibility criteria may be randomized in a 1:1:1 ratio into 1 of the following treatment groups:

Treatment Group 1: continued SOC therapy together with IV RDV 200 mg on Day 1 followed by IV RDV 100 mg on Days 2, 3, 4, and 5

Treatment Group 2: continued SOC therapy together with IV RDV 200 mg on Day 1 followed by IV RDV 100 mg on Days 2, 3, 4, 5, 6, 7, 8, 9, and 10

Treatment Group 3: continued SOC therapy

In Part B, an additional approximately 1000 participants who meet all of the eligibility criteria may receive:

Extension Treatment Group: continued standard of care therapy together with IV RDV 200 mg on Day 1 followed by IV RDV 100 mg on Days 2, 3, 4, 5, 6, 7, 8, 9, and 10 unless treatment Group 1 of Part A is selected. If treatment for 5 days is selected, all participants in the Extension Treatment Group and all new participants will be reassigned to receive treatment for a total of 5 days. National and local regulatory authorities will be informed.

Participants in Part A of the study will be the primary efficacy population. Participants enrolled in Part B, will have data reported descriptively at study completion.

3.4. Duration of Treatment

Participants will receive study treatment with RDV for 5 days (treatment group 1), study treatment with RDV for 10 days (treatment group 2), no RDV (treatment group 3), or either 5 or 10 days (Extension Treatment Group). If the participant is discharged, RDV treatment will stop at that time.

3.5. Discontinuation Criteria

Study drug dosing in an individual subject will be placed on hold and may be discontinued, following a review of all available clinical data by the medical monitor and discussion with the investigator, if any of the following occurs:

- Any SAE or \geq Grade 3 AE suspected to be related to RDV
- Any elevations in ALT $> 5 \times$ ULN; or ALT $> 3 \times$ ULN and total bilirubin $> 2 \times$ ULN, confirmed by immediate repeat testing
- Creatinine Clearance < 30 mL/min

Discontinuation of study medication is not a seriousness criterion.

Subjects who discontinue the study medication should be encouraged to remain in the study and attend study visits as described in Sections 6.3, 6.4, and 6.5.

3.6. End of Study

The end of the study will be the last participant's last observation (or visit).

3.7. Post Study Care

The long-term care of the participant will remain the responsibility of their primary treating physician. Remdesivir is being supplied with curative intent. There is no provision for post-study availability.

4. SUBJECT POPULATION

4.1. Number of Subjects and Subject Selection

In Part A, approximately 600 participants will be randomized in a 1:1:1 ratio into 1 of 3 treatment groups. In Part B, up to approximately 1000 participants may be assigned into a single treatment group. Rescreening may occur at the investigator's discretion.

4.1.1. Subject Replacement

Subjects who discontinue prior to the end of study will not be replaced.

4.2. Inclusion Criteria

Subjects must meet all of the following inclusion criteria to be eligible for participation in this study:

- 1) Willing and able to provide written informed consent (participants ≥ 18 years of age) or assent (participants ≥ 12 and < 18 years of age) prior to performing study procedures. For participants ≥ 12 and < 18 years of age, a parent or legal guardian willing and able to provide written informed consent prior to performing study procedures
- 2) Aged ≥ 18 years (at all sites), or aged ≥ 12 and < 18 years of age weighing ≥ 40 kg (where permitted according to local law and approved nationally and by the relevant institutional review board [IRB] or independent ethics committee [IEC])
- 3) SARS-CoV-2 infection confirmed by PCR ≤ 4 days before randomization
- 4) Currently hospitalized and requiring medical care for COVID-19
- 5) SpO₂ $> 94\%$ on room air at screening
- 6) Radiographic evidence of pulmonary infiltrates
- 7) Men and women of childbearing potential who engage in heterosexual intercourse must agree to use protocol specified method(s) of contraception as described in [Appendix 3](#).

4.3. Exclusion Criteria

Subjects who meet *any* of the following exclusion criteria are not to be enrolled in this study:

- 1) Participation in any other clinical trial of an experimental agent treatment for COVID-19
- 2) Concurrent treatment or planned concurrent treatment with other agents with actual or possible direct acting antiviral activity against SARS-CoV-2

3) Requiring mechanical ventilation at screening

4) ALT or AST > 5 × ULN

Note: if per local practice only ALT is routinely measured, exclusion criteria will be evaluated on ALT alone

5) Creatinine clearance < 50 mL/min using the Cockcroft-Gault formula for participants ≥ 18 years of age {[Cockcroft 1976](#)} and Schwartz Formula for participants < 18 years of age

6) Positive pregnancy test ([Appendix 3](#))

7) Breastfeeding woman

8) Known hypersensitivity to the study drug, the metabolites, or formulation excipient

5. INVESTIGATIONAL MEDICINAL PRODUCTS

5.1. Randomization, Blinding, and Treatment Codes Access

5.1.1. Randomization

Subjects who meet eligibility criteria will be randomized in a 1:1:1 ratio to 1 of 3 treatment groups on Day 1 using an IWRS, and assigned a subject number. Randomization will not be stratified.

5.1.2. Blinding

Blinding of treatment assignments or data will not be performed in this study.

5.2. Description and Handling of Remdesivir

5.2.1. Formulation

Remdesivir for injection, 100 mg, is a preservative-free, white to off-white to yellow, lyophilized solid containing 100 mg of GS-5734 that is to be reconstituted with sterile water for injection and diluted into 0.9% saline prior to administration by IV infusion.

In addition to the active ingredient, RDV for injection, 100 mg, contains the following inactive ingredients: betadex sulfobutyl ether sodium (SBECD), water for injection, hydrochloric acid, and sodium hydroxide. Hydrochloric acid and sodium hydroxide are used to adjust the formulation to a pH of 3.0 to 4.0.

5.2.2. Packaging and Labeling

Remdesivir for injection, 100 mg, is supplied as a sterile product in a single-use, 30 mL Type I clear glass vial. Each vial is sealed with a fluoro-resin laminated rubber stopper and an aluminum overseal with a red, plastic flip-off cap.

Remdesivir for injection, 100 mg, shall be labeled to meet all applicable requirements of the US Food and Drug Administration (FDA), EU Guideline to Good Manufacturing Practice - Annex 13 (Investigational Medicinal Products), the J-GCP (Ministerial Ordinance on Good Clinical Practice for Drugs), as applicable, and/or other local regulations.

5.2.3. Storage and Handling

Remdesivir for injection, 100 mg, should be stored below 30 °C (86 °F) prior to use. Storage conditions are specified on the label. Until dispensed for dosing, all vials of study drugs should be stored in a securely locked area, accessible only to authorized site personnel.

To ensure the sterility, stability, and proper identification, study drug(s) should not be stored in a container other than the container in which they were supplied.

Measures that minimize drug contact with the body should always be considered during handling, preparation, and disposal procedures.

Remdesivir for injection, 100 mg, is recommended to be reconstituted and diluted on the same day as administration. Remdesivir for injection, 100 mg, does not contain any preservative and is intended for single-use. Any unused RDV material should be discarded.

5.3. Dosage and Administration of Remdesivir

Remdesivir for injection, 100 mg, will be provided by Gilead. In Part A, participants in Treatment Groups 1 and 2 will receive RDV 200 mg on Day 1 followed by IV RDV 100 mg on Days 2, 3, 4, and 5. Participants in Treatment Group 2 will also receive RDV 100 mg on Days 6, 7, 8, 9, and 10. In Part B, participants in the Extension Treatment Group will receive RDV 200 mg on Day 1 followed by IV RDV 100 mg on Days 2, 3, 4, 5, 6, 7, 8, 9, and 10. If Treatment Group 1 of Part A is selected for Part B, or if treatment for 5 days is selected in a study of more severe disease, all participants in the Extension Treatment Group and all new participants will be reassigned to receive treatment for a total of 5 days. Remdesivir treatment will be stopped at discharge regardless of the scheduled duration of therapy. Remdesivir will be administered over 30 minutes where possible.

5.4. Accountability for Investigational Medicinal Product

The investigator is responsible for ensuring adequate accountability of all used and unused study drug. This includes acknowledgment of receipt of each shipment of study drug (quantity and condition).

Each study site must keep accountability records that capture:

- The date received and quantity of study drug kits
- The date, subject number, and the study drug kit number dispensed
- The date, quantity of used and unused study drug returned, along with the initials of the person recording the information

5.4.1. Investigational Medicinal Product Return or Disposal

Gilead recommends that used and unused study drug supplies be destroyed at the site. If the site has an appropriate SOP for drug destruction as determined by Gilead, the site may destroy used (empty or partially empty) and unused study drug supplies in accordance with that site's approved SOP. A copy of the site's approved SOP will be obtained for eTMF. If study drug is destroyed on site, the investigator must maintain accurate records for all study drugs destroyed. Records must show the identification and quantity of each unit destroyed, the method of destruction, and the person who disposed of the study drug. Upon study completion, copies of the study drug accountability records must be filed at the site. Another copy will be returned to Gilead.

If the site does not have an appropriate SOP for drug destruction, used and unused study drug supplies are to be sent to the designated disposal facility for destruction. The study monitor will provide instructions for return.

The study monitor will review study drug supplies and associated records at periodic intervals.

For both disposal options listed above, the study monitor must first perform drug accountability during an on-site monitoring visit.

5.5. Prior and Concomitant Medications

Concomitant use of the following is prohibited in participants receiving RDV:

- Traditional herbal treatments including herb sho-saiko-to (or Xiao-Shai-Hu-Tang)
- Investigational agents with putative antiviral activity for COVID-19 including approved HIV protease inhibitors such as lopinavir/ritonavir, chloroquine, interferon, etc.

Concomitant use of investigational agents such as approved HIV protease inhibitors like lopinavir/ritonavir, chloroquine, etc while receiving RDV is prohibited due to lack of evidence on additive or synergistic effects and potential for an increased risk of transaminase elevations.

Medications will be assessed only from Day 1 prior to enrollment to Day 28 or discharge, whichever is earlier.

6. STUDY PROCEDURES

The study procedures to be conducted for each subject enrolled in the study are presented in tabular form in [Appendix 2](#) and described in the text that follows.

The investigator must document any deviation from the protocol procedures and notify the Gilead or contract research organization (CRO).

6.1. Subject Enrollment and Treatment Assignment

Entry into screening does not guarantee enrollment into the study. In order to manage the total study enrollment, Gilead, at its sole discretion, may suspend screening and/or enrollment at any site or study-wide at any time.

6.2. Pretreatment Assessments

6.2.1. Screening Visit

Subjects will be screened within 2 days before randomization and dosing to determine eligibility for participation in the study.

- Obtain written informed consent or assent (age ≥ 12 to < 18 , where locally and nationally approved)

After the informed consent the following assessments are performed to determine eligibility requirements as specified in the inclusion and exclusion criteria:

- Focused medical history including the following information (eg, date of first symptoms, overall symptoms, exposure source, demographics, baseline characteristics, allergies and medical history)
- Review and record medications and therapies for this current illness
- Counsel subjects to use adequate birth control methods required during the trial to avoid pregnancy
- Targeted physical examination including, vital signs (heart rate, temperature, blood pressure), body weight, and height
- Documentation of respiratory status:

Respiratory Rate

- Oxygen supplementation: room air, low flow O₂ (L/min and %), high flow O₂ (L/min and %), CPAP/BIPAP (FiO₂ or %), mechanical ventilation (FiO₂ or %), ECMO

Oxygenation: SpO₂ or PaO₂

Radiographic findings

- Obtain blood samples if not done in the preceding 48 hours for creatinine, creatinine clearance, ALT and AST
- Pregnancy test (for women of childbearing potential)
- Record any serious adverse events and all adverse events related to protocol-mandated procedures occurring after signing of the consent (or assent) form.

Study subjects who qualify should be immediately randomized. Randomization and dosing should occur on the same day if possible.

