6.2.2. Baseline/Day 1 Assessments

The following evaluations are to be completed at the Day 1 visit. The investigator must have confirmed eligibility before proceeding with randomization on the Day 1 visit. If the screening and Day 1 visits occur within 24 hours, no procedures need to be repeated. Participants must complete the following assessments before being administered study drug:

- Physical examination including, vital signs (heart rate, temperature, blood pressure, and body weight)
- Documentation of respiratory status:

Respiratory rate

— Oxygen supplementation: room air, low flow O₂ (L/min and %), high flow O₂ (L/min and %), CPAP/BIPAP (FiO₂ or %), mechanical ventilation (FiO₂ or %), ECMO

Oxygenation: SpO₂ or PaO₂

Radiographic findings (if available)

- Review AEs and document concomitant medications
- Obtain blood samples for white blood cell count, hemoglobin and/or hematocrit, platelets, creatinine and creatinine clearance, glucose, total bilirubin, ALT, AST

- SARS-CoV-2 Testing: Collect nasopharyngeal swab sample for subjects/sites participating in this portion of the study
- Review Ordinal Scale (Section 6.9)

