In addition, even if not performed as standard of care, WBC count, hemoglobin and/or hematocrit, platelets, creatinine, creatinine clearance, glucose, total bilirubin, ALT, and AST will be performed at Days 1, 3, 5, 8, 10, and 14 or until discharge, whichever is earlier.

Additional SARS-CoV-2 testing may be conducted at selected sites. At participating sites, nasopharyngeal swab samples will be collected at Days 1, 3, 5, 8, 10, and 14, sent to a central laboratory, and assayed using quantitative reverse transcriptase PCR to quantify SARS-CoV-2

viral load. Pretreatment and posttreatment samples with detectable SARS CoV-2 may be sequenced for resistance monitoring of the viral polymerase gene.

Randomization

For Part A, participants who met eligibility criteria were randomized in a 1:1:1 ratio to 1 of 3 treatment groups on Day 1 using an IWRS, and assigned a subject number. Randomization is not stratified. Part B is not randomized.

Sites

Up to approximately 160 centers globally.

Duration of Treatment

Participants in Part A received study treatment with RDV for 5 days (Treatment Group 1), 10 days (Treatment Group 2) or no RDV (Treatment Group 3). In Part B, Participants will receive 10 days (Extension Treatment Group) of RDV. If the participant is discharged, RDV treatment will end at that time.

Discontinuation Criteria

Study drug dosing in an individual participant will be placed on hold and may be discontinued, following a review of all available clinical data by the medical monitor and discussion with the investigator, if any of the following occurs:

- Any serious adverse event (SAE) or \geq Grade 3 AE suspected to be related to RDV.
- Any elevations in ALT > $5 \times \text{ULN}$; or ALT > $3 \times \text{ULN}$ and total bilirubin > $2 \times \text{ULN}$, confirmed by immediate repeat testing
- Creatinine clearance < 30 mL/min

End of Study

The end of the study will be the last participant's last observation (or visit).

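### Bilirubin is neither an entry criterion nor a named screening blood, so a participant already in the ALT–bilirubin hold range can be randomized or enter Part B, and can receive the loading dose

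*Protocol*

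**What the plan says.** **Entry.** The only liver-test limit in Protocol 4.3 is "ALT or AST > 5 × ULN", with a note that ALT alone suffices where AST is not routine locally. Bilirubin appears in none of the seven inclusion or eight exclusion criteria.

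**Screening.** Protocol 6.2.1 tells sites to "Obtain blood samples if not done in the preceding 48 hours for creatinine, creatinine clearance, ALT and AST". The synopsis names the same four tests. Section 6.2.1 continues: "Study subjects who qualify should be immediately randomized", with dosing on the same day where possible.

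**Day 1.** Protocol 6.2.2 states: "The investigator must have confirmed eligibility before proceeding with randomization on the Day 1 visit". It adds: "Participants must complete the following assessments before being administered study drug". The Day 1 list includes a blood sample for total bilirubin, ALT and AST. This is the first visit at which bilirubin is listed.

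**Hold rule.** Under Protocol 3.5, "Study drug dosing in an individual subject will be placed on hold and may be discontinued" when ALT is above 5 × ULN, or when ALT is above 3 × ULN with total bilirubin above 2 × ULN, "confirmed by immediate repeat testing". SAP 1.2 carries the same rule into Part B: "Study drug dosing in an individual participant will be placed on hold and may be discontinued".

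**The concern.** The rule that stops dosing has two hepatic limbs, and the entry rule mirrors only one. ALT alone above 5 × ULN is both an exclusion and a hold. The combined ALT and bilirubin limb has no counterpart at entry, and the test it depends on is not named among the screening bloods. A site that follows the text can confirm eligibility, randomize at once, and only then learn that the participant meets a condition for holding the drug.

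This is a safety and consistency issue. Section 1.5 names transient, low-grade transaminase elevation as the specific risk. It relies on two protections: restricting who enters, and monitoring liver tests afterwards. For this group the first does not operate, and the second may act only after the loading dose has been given.

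**Working it through.** The plan states no figure on this point. The check is a comparison of thresholds, followed by short dose arithmetic.

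**Step 1. Compare entry and hold limits** (AST taken as no more than 5 × ULN where measured).

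| Baseline pattern | Entry (4.3) | Hold (3.5) | Consistent? |
|---|---|---|---|
| ALT > 5 × ULN | Excluded | Hold | Yes |
| ALT > 3 and ≤ 5 × ULN, bilirubin > 2 × ULN | Allowed | Hold once confirmed | **No** |
| ALT > 3 and ≤ 5 × ULN, bilirubin ≤ 2 × ULN | Allowed | No hold | Yes |
| ALT ≤ 3 × ULN | Allowed | No hold | Yes |
| Creatinine clearance < 50 mL/min | Excluded | Hold only below 30 mL/min | Yes; entry is stricter |

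An ALT of exactly 5 × ULN is allowed, because the exclusion applies only above that value. Among the laboratory hold rules, only the combined limb can already be met by someone who passes the entry criteria.

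**Step 2. Look for text that closes the gap before the first dose.**

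- *Section 6.2.2* requires the Day 1 sample to be obtained before study drug. It does not say the result must be back, or compared with Section 3.5, before infusion. Its allowance not to repeat procedures done within 24 hours does not clearly remove this draw, since bilirubin was not named at screening.
- *Section 6.6* requires laboratory assessments at screening, but gives its bilirubin-containing list only from Day 1 to Day 14. Its instruction to use the most recent pre-dose result sits with the data-entry rules and sets no condition for dosing.
- *Appendix 2* has one laboratory row marked for both screening and Day 1, without listing analytes.
- *Section 3.5* governs dosing, not eligibility. It cannot prevent randomization, and it takes effect after a repeat test.

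If the Day 1 result and its repeat are back in time, Section 3.5 can stop the first dose. If they are not, nothing in the text prevents it.

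**Step 3. Exposure that follows directly.** Doses are from Section 5.3.

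- 5-day course: 200 + 4 × 100 = 600 mg
- 10-day course: 200 + 9 × 100 = 1100 mg
- Loading dose as a share: 200/600 = 33.3%; 200/1100 = 18.2%

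This applies to the two remdesivir groups of Part A and to Part B. A standard-of-care participant with the same pattern can be randomized but receives no remdesivir.

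**The case against.** The strongest reply is that the protocol largely handles this before the first dose. Participants are inpatients, testing is local, ALT and bilirubin must be drawn on Day 1 before drug, and Section 3.5 asks for an immediate repeat. A sensible investigator would not infuse once a hold criterion is met. That stands as a substantial partial safeguard. It leaves two things open: no sentence makes review of the result a condition for the first dose, and randomization or Part B entry has already happened.

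Second, the screening panel is somewhat ambiguous. Appendix 2 and Section 6.6 require laboratory tests at screening, and the synopsis introduces its list as non-exhaustive. Some sites may therefore measure bilirubin then. That also stands, so the accurate statement is that bilirubin is not named for screening. Even where it is measured, no criterion would exclude the participant.

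Third, entry and hold limits need not be identical, as creatinine clearance shows. True, but there the entry limit is the stricter one, so nobody is admitted already in the hold range.

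Stronger readings that a reader might infer are not supported:

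- *Larger exposure.* Reaching 200 + 100 = 300 mg needs the Day 1 result or its immediate repeat to be still outstanding at the Day 2 dose. Reaching 200 + 2 × 100 = 400 mg needs the Day 1 result to go unused and the Day 3 test to be confirmed only after that day's dose. Both depend on slow or non-compliant follow-up, not on the entry criteria.
- *Bias in the efficacy analysis.* A remdesivir participant held and never dosed would leave the Full Analysis Set, while a similar standard-of-care participant stays. That comes from the definition in Section 8.3.1.1, applies to any never-dosed participant, and is a separate matter.
- *Demonstrated harm.* Section 1.5 describes the transaminase elevations after multiple daily doses. Nothing in the documents ties a single loading dose to injury in this group.

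**Conclusion.** The point holds as a modest safety and consistency gap, worth considering. As written, the rules allow a participant with ALT above 3 and up to 5 × ULN and total bilirubin above 2 × ULN to qualify and be randomized, or to enter Part B, while already meeting a hold criterion. They do not ensure that this is recognized before the loading dose.

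The size that follows directly is one 200 mg dose per affected remdesivir participant, 33% of the 5-day or 18% of the 10-day course. These shares describe exposure, not clinical importance. The documents give no frequency for the pattern, so no number of participants is claimed, and no effect on the efficacy result is claimed.

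The conclusion assumes that Section 6.2.1, as the most specific text, defines the screening bloods, and that a Day 1 result and its repeat may not always be back before a same-day infusion.

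**What to change.** Three changes to the protocol text:

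1. In Section 6.2.1 and the synopsis, add total bilirubin to the screening bloods, resulted with ALT before randomization or Part B entry. Keep the Day 1 sample unless screening was within 24 hours.
2. In Section 4.3, add an exclusion for ALT above 3 × ULN combined with total bilirubin above 2 × ULN, applied to all three Part A groups and to Part B.
3. In Section 6.2.2, state that ALT and bilirubin results must be checked against Section 3.5 before the first dose.

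The third change alone would address the loading dose. The first two also stop people in the hold range from being randomized or enrolled. Since the SAP describes Part A as already randomized, the practical benefit lies mainly in Part B, where every participant is assigned remdesivir.

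**Cost.** Bilirubin is already required on Day 1, but simply moving that test to screening would not always be free. When screening is more than 24 hours before Day 1, or a site relies on results from the preceding 48 hours that lack bilirubin, an extra test is needed. There is also a short wait for the result, against the aim of immediate randomization, and a few more screen failures.
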